#### **2.1.2 Secondary**

Secondary endpoints to be measured include NEC and ELF for inflammatory endpoints, spirometry for change from baseline, change in cardiovascular endpoints FMD, HRV and LV ultrasound in FA vs O3.

Exploratory endpoints correlation of ambient ozone level using a novel, wearable device.

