4. **Spirometry:** Standard spirometry to obtain FEV1 and FVC measurements will be done prior to sputum induction. This is done by having the subject exhale forcefully and completely into a mouth piece attached to a pneumotach. This will be repeated several times, and the procedure will be done following ATS/ERS standards.
5. **Flow-mediated brachial artery dilation (FMD):** This measurement is made by imaging the brachial artery with an ultrasound device. The blood flow to the artery is occluded for 5 minutes, and the artery is again imaged when blood flow is resumed.
6. **Left ventricular strain:** Left ventricular contractility will be assessed by measuring global longitudinal strain using 2-dimensional speckle tracking echocardiography. Apical 4-chamber, 2-chamber, and long axis 2-dimensional ultrasound images of the heart will be acquired using a Philips EPIQ 7 ultrasound machine and stored for subsequent off-line analysis. Global longitudinal strain will be quantified using Philips QLAB advanced quantification software.

The subject will be discharged to home with contact information for a study physician who is on-call if the subject has any health concerns. The subject will return the next morning, and after health history is updated and vital signs collected, the following will take place:

1. **Heart rate variability (HRV):** Standard ECG leads will be placed on the subject's chest, and connected to a monitor that records the heart rate and rhythm. The subject will be asked to lie supine in a quiet, darkened room for up to 30 minutes. The subject will do this before the exposure and immediately after the exposure. The analysis for this measurement is computer based.
2. **Spirometry:** Standard spirometry will be measured prior to the subject entering the exposure chamber.
3. **Ozone monitor:** Subjects will wear an experimental ozone monitor, which is on a bracelet. This is to validate the wearable monitor in an environment with known ozone concentration.
4. **Telemetry:** Standard 3 lead ECG monitoring will be done while the subject is in the exposure chamber.
5. **Symptom questionnaire:** Subjects will be asked to complete a symptom questionnaire prior to entering the chamber.
  

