7. The subject will enter the chamber. The atmosphere will be determined randomly and will be either filtered clean air or ozone. The ozone concentration will be varied from 0.06 to 0.08 through the course of the exposure, and the exposure will last for 6.5 hours. The subjects will rest during the exposure with intermittent mild walking on the treadmill. Subjects will be provided with a low fat lunch to eat while they are in the chamber. HR will be monitored continually while the subject is in the chamber, and blood pressure will be measured hourly. A symptom questionnaire will be completed at the end of the exposure period. Immediately upon exiting the chamber, the subjects will undergo HRV for up to 30 minutes, followed by FMD and LV strain measurement. ELF and NL samples will be collected. Nasal epithelial cells (NEC) will be obtained from the opposing nostril from screening or exposure session 1.

Spirometry will be obtained prior to discharge, and at any point during the study if the subject experiences any distress or shortness of breath. Subjects will be discharged with contact information for a study physician on call.

Subjects will return 24 hours later. After updating the health history and collecting vital signs, the following measurements/samples will be collected:

1. Symptom questionnaire
2. HRV for up to 30 minutes
3. Venipuncture as collected at screening day

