## 7 DATA ANALYSIS

Aim 1. Characterize ozone induced changes in nasal PMN counts.

This is a randomized, double blind, crossover pilot study, studying the changes in cells of nasal lavage (neutrophilla) after low-level ozone exposure. First, descriptive analysis will be conducted to examine potential ozone exposure effect and period effect. Second, two sample tests such as t-test and Mann Whitney test will be used to compare changes in response in clean air and ozone exposure groups. In general, carry-over effect is first tested. In the absence of significant carry-over effect, pooled data from both periods can be used to estimate the ozone exposure effect. Otherwise, only period 1 data can be used. We will report effect estimates, standard deviation as well as confidence intervals for ozone exposure effect and potential period effect. Finally, a random effects model will be fitted to assess the ozone exposure effect. Confidence intervals will be reported.

Aim 2. Characterize ozone induced changes in inflammatory cytokines in nasal epithelial cell (NEC) biopsy and nasal epithelial lining fluid ELF

The analysis plan is the same as in Aim 1.

Aim 3. Characterize ozone induced changes in FMD, HRV, LVS, Brachial artery ultrasound, ambulatory ECG measures, & other cardiovascular measures.

The analysis plan is the same as in Aim 1.

Aim 4. Characterize ozone induced changes in spirometric measures

The analysis plan is the same as in Aim 1.

Aim 5. Investigate the performance of a wearable monitor for ambient ozone measurement.

There are 2 current devices which will be used (descriptions and photos attached. The subject may wear one or both of these devices. The purpose of these devices at this time is strictly to assess the measured values obtained by the devices compared to the known O3 atmosphere. However, as these devices are prototypes there are two important questions. The

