first is will the sensors technically perform appropriately thought the exposure while being worn by volunteers. In essence, the goal of this assessment is to simply see fi the devices work at all, and to identify specific technical modifications which may need to be made. The second goal is to determine if the readings of functioning wearable sensors correlate well with the readings of the standard ozone monitors present in the exposure chamber (that is to demonstrate that they are accurate). All of the ozone sensors are non-invasive. **These are exploratory endpoints**

In case of potential missing data, we will first carefully investigate the pattern of missing data and determine if it is informative missing. In case the missing is heavy, we will explore statistical methods such as multiple imputation to handle the missing data issue (Little and Rubin, 2014).

The pilot design and sample size is motivated by our earlier similar study (Peden et al, 1995). The goal of this pilot study is to determine whether low-level ozone affects a) nasal epithelial inflammation, and b) exploratory cardiovascular endpoints such as heart rate variability. If we find that cardiovascular endpoints are affected by low-level ozone in this small group, further studies will explore these, and perhaps other, cardiovascular markers and outcomes. The aim of these future studies will be to further characterize the cardiovascular effects of low-level ozone exposure.

The sample size for this study is determined on our primary endpoint outlined in Aim 1. The other aims are all secondary analysis using the same sample collected in Aim 1. We will not collect additional subjects for Aims 2-5. In previous literature, it is found that higher-level shorter duration ozone exposure caused a change in neutrophilia of 67 with a standard deviation of 31, while the change is 31 with a standard deviation of 17 in the clean-air group (Peden et al, 1995). The aimed effect size is 36. If we assume the significance level is at 0.05, a sample size of 13 subjects is adequate to ensure 90% power of detecting the effect. Approximately half of the subjects will receive air-ozone sequence, and another half will receive ozone-air sequence. Using a significance level of 0.05, the table below shows the sample size under various potential correlation coefficient. The calculation is based on a two-sided paired t test.

Effect size	Correlation coefficient	Power	N
36	0	0.8	10
	0	0.9	13
	0.3	0.8	8
	0.3	0.9	10

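### Minor: Aim 5 takes good correlation with the chamber monitors as proof of sensor accuracy, but correlation cannot show a constant offset or separate scale error from noise

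*Combined protocol and SAP*

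**What the plan says.** Section 7, Aim 5 sets two questions for the prototype sensors. The first is whether they function while worn. The second is whether the readings of functioning sensors "correlate well with the readings of the standard ozone monitors present in the exposure chamber (that is to demonstrate that they are accurate". The parenthesis makes correlation the evidence for accuracy. Section 2.1.2 agrees: "Exploratory endpoints correlation of ambient ozone level using a novel, wearable device".

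Two other places state a wider purpose. Aim 5 opens by saying that the devices are used "strictly to assess the measured values obtained by the devices compared to the known" ozone atmosphere, and Section 4 says of the bracelet monitor: "This is to validate the wearable monitor in an environment with known ozone concentration". Neither names a statistic.

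Aims 2 to 4 refer back to the Aim 1 analysis, but Aim 5 does not, so correlation is the only analysis it names. The plan gives no mean difference, limits of agreement, calibration line, concordance measure or acceptance threshold. It does not say whether filtered-air and ozone readings are analysed together. On status it is clear: "These are exploratory endpoints".

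**The concern.** Accuracy means that the sensor shows the same value as the reference. Correlation asks only whether the two move together along some straight line, whatever its slope and intercept. A sensor with a large systematic error could therefore satisfy Aim 5 as worded and be described as accurate.

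The distinction also matters for the other stated goal of Aim 5, to "identify specific technical modifications which may need to be made". A constant offset or a scale error can be removed by recalibration, and random noise cannot. Correlation hides the offset and merges the other two.

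Pooling adds a further problem. One session is filtered air, and in the other "The ozone concentration will be varied from 0.06 to 0.08 through the course of the exposure". If both are combined, the gap between the two atmospheres dominates the variance, and a high r may show little more than that the device can tell ozone from clean air.

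**Working it through.** Aim 5 states no sample size, threshold or expected correlation, so there is no figure of the plan to reproduce.

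**Inputs**

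- From the documents: ozone between 0.06 and 0.08 ppm (Protocol Summary; Section 4), midpoint 0.07; the other session is filtered air (Section 4).
- Assumed, for illustration: ozone spread evenly over 0.06 to 0.08; filtered air at 0 ppm; equal numbers of readings in the two sessions; the sensor noise SDs given below.

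**Formula.** Let the sensor read Y = a + kX + e, where X is the true ozone, a the offset, k the scale and s the SD of the noise e. Then

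r = k·SD(X) / √(k²·Var(X) + s²).

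The offset a does not appear, and k and s enter only through s/k.

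**Step 1: no noise, documented range only.** With k = 0.5 and s = 0, r = 1.00. The error is −0.5X: −0.03 ppm at 0.06, −0.04 ppm at 0.08, and −0.035 ppm at the midpoint. This step needs no assumed noise.

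**Step 2: spread of the reference.**

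- Within ozone: Var(X) = 0.02²/12 = 3.33×10⁻⁵, SD 0.00577 ppm.
- Pooled: Var(X) = 0.5 × 3.33×10⁻⁵ + 0.25 × 0.07² = 1.242×10⁻³, SD 0.0352 ppm.

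**Step 3: three sensors with the same s/k = 0.006.**

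- Within ozone: r = 0.00577/√(3.33×10⁻⁵ + 0.006²) = 0.693.
- Pooled: r = 0.0352/√(1.242×10⁻³ + 0.006²) = 0.986.

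The difference Y − X has mean a + (k − 1) × 0.07 and variance (k − 1)²·Var(X) + s². The 95% limits are the mean ± 1.96 SD.

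| Sensor | r within ozone | r pooled | Mean difference in ozone (ppm) | 95% limits (ppm) | Slope |
|---|---|---|---|---|---|
| k = 0.5, s = 0.003, a = 0 | 0.693 | 0.986 | −0.035 | −0.043 to −0.027 | 0.5 |
| k = 1, s = 0.006, a = 0 | 0.693 | 0.986 | 0 | −0.012 to +0.012 | 1 |
| k = 1, s = 0.006, a = +0.02 | 0.693 | 0.986 | +0.020 | +0.008 to +0.032 | 1 |

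For the first row, SD = √(0.25 × 3.33×10⁻⁵ + 0.003²) = 0.00416, and 1.96 × 0.00416 = 0.0082. For the other two, 1.96 × 0.006 = 0.0118.

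Correlation cannot tell these three sensors apart. The mean difference and the slope can.

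**Step 4: equal noise.** With s = 0.005 within ozone, r = 0.50 for k = 0.5 and 0.76 for k = 1. A scale error can therefore lower r. But k = 1 with s = 0.010 also gives r = 0.50, so the value does not show the cause.

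**Step 5: shape of the exposure.** If ozone moves in three equal steps (0.06, 0.07, 0.08; SD 0.00816), the sensors in the table again share one r: 0.806 within ozone and 0.986 pooled. The conclusion does not depend on an even spread.

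**The case against.** The strongest reply is that a loose phrase is being read as a specified statistic. No coefficient or threshold is named, and the purposes quoted from Aim 5 and Section 4 suggest that agreement is intended. A device that shows 0.035 ppm in a chamber known to hold 0.07 would be noticed by anyone who compared the values. This limits the consequence but does not remove the problem. Those passages state a purpose without a method, and the only criterion given for accuracy, repeated in the endpoint list, is correlation.

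A second reply is that r suits a first screen of prototypes. Because r depends on s/k, it ranks sensors by the noise that would remain after recalibration. The first two sensors in the table would indeed be equivalent once recalibrated. This is a fair defence of reporting r. It does not justify calling the devices accurate, and r supplies neither the offset nor the scale needed to recalibrate them.

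Third, only an offset common to all readings leaves r unchanged. Offsets that vary between units or subjects lower it. With s = 0.006 and an assumed offset SD of 0.01 ppm, r falls from 0.69 to 0.44 within ozone, and from 0.986 to 0.949 pooled. That is correct, and the claim here is confined to a constant offset.

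Finally, the device descriptions are an attachment, and chamber procedures sit in a separate operations plan (Section 3.6). Output units, logging interval and any existing calibration are not in the text, so every figure that involves noise is hypothetical.

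**Conclusion.** The concern holds, as a minor point. Followed as written, Aim 5 could call a sensor accurate when it under-reads ozone by half, with r = 1.00 and an error of 0.03 to 0.04 ppm. That result rests only on the documented range. The figures with noise rest on assumed noise SDs, filtered air at 0 ppm and equal numbers of readings. They illustrate the size of the effect and do not predict how these devices will perform.

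The grade stays minor because the aim is exploratory, the devices are prototypes and no pass mark is set. No primary or secondary endpoint, sample size or safety rule depends on the result.

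**What to change.** In Section 2.1.2 and in Aim 5 of Section 7, replace correlation with agreement as the criterion for accuracy:

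- Analyse each device separately, since "The subject may wear one or both of these devices".
- Report the mean difference (sensor minus chamber monitor) with 95% limits of agreement, separately for ozone and filtered-air sessions, allowing for repeated readings within subject.
- Report the calibration slope and intercept within the ozone sessions. Take the offset mainly from the filtered-air mean difference and not from that intercept.
- If a device does not output ppm, report the calibration line and its residual error instead.
- Keep correlation as a description, and state whether it is pooled or within session.

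The cost is one or two sentences and a little extra analysis. Correlation already requires time-matched readings, so no further subjects, visits or measurements are needed.

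The limitation is precision, because the ozone sessions span only 0.02 ppm. Assuming 100 independent readings and noise SD 0.006 ppm:

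- The slope has standard error 0.006/(0.00577 × √100) = 0.10.
- The intercept has standard error 0.006 × √(1/100 + 0.07²/(100 × 3.33×10⁻⁵)) = 0.0073 ppm, because it extrapolates to zero.

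Readings within a subject are unlikely to be independent, so the true standard errors would probably be larger. The mean difference and its limits do not depend on this slope.
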